Disease evaluation by Response Evaluation Criteria in Solid Tumours (RECIST) v1.1 and immune RECIST (iRECIST) (solid tumours only)		X h			X i		X i	X i	X i	h. Scans within 4 weeks of screening will be accepted. i. Using standard of care scan schedule for the specified solid tumour. The first radiographic scan after receiving SUPLEXA will be performed at Week 6-12 weeks after the 1st SUPLEXA infusion and thereafter every 6-12 weeks depending on tumour type and as clinically indicated per investigator's discretion.

Study period	Screening		Treatment Period (Weekly dosing)		TREATMENT GAP	Treatment Extension Period	Follow Up after last dose		Notes	
			SUPLEXA Batch 1							
Study Treatment Week	-5	-5 to -1	First 3 infusions	Additional doses 		Doses 				
Visit Window (days)		±2		±2		60	-1 to +7	±5		
			Week 0 Day 1/ Baseline	1, 2			Every 8 weeks up to 48 weeks from last dose	EOS/ET	End of Study (EOS) will be conducted within 30d for all subjects who completed the study per protocol; Early termination (ET) visit will be conducted within 30d or subjects who withdraw from the study prematurely.	
Disease evaluation for haematologic malignancies only		X		X*		X*	X*	X	*As clinically indicated, may also be conducted every 4 weeks, starting 4 weeks after the 3 rd dose	
Complete blood count (CBC) with differential and blood chemistry	X		X j	X j, k	X j	X j	X	X	Refer to Table 5 for list of parameters to be evaluated j. Predose k. Repeat at baseline in local hospital lab for stat results, and central lab sample to be shipped	
Collect blood for pharmacodynamic immune assessments, including cytokines			X	X	X	X	X l		Refer to Section 8.4 for list of parameters to be evaluated l. collected where possible post dose	

Study period	Screening		Treatment Period (Weekly dosing)		TREATMENT GAP	Treatment Extension Period	Follow Up after last dose		Notes	
			SUPLEXA Batch 1							
Study Treatment Week	-5	-5 to -1	First 3 infusions	Additional doses 		Batch 2				
			Week 0 Day 1/ Baseline	1, 2		Doses 				
Visit Window (days)		±2		±2	±2	-1 to +7	60	-1 to +7	Every 8 weeks up to 48 weeks from last dose	EOS/ET
Serology		X m							Refer to Table 5 for list of parameters to be evaluated	

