### 3 OBJECTIVES AND ENDPOINTS

Objectives	Endpoints
Primary	

 
To assess safety and tolerability of SUPLEXA in subjects with malignant solid tumour and haematologic malignancies.
 
	
 
Incidence of dose limiting toxicities (DLTs) (as described in Section 6.5.1).
 
Incidence of adverse events (AEs), and serious adverse events (SAEs) overall, by severity, by relationship to each study intervention, and those that led to discontinuation of study intervention.
 

Secondary 
 
Solid tumours cohort: To assess the efficacy of SUPLEXA in subjects with malignant solid tumour as assessed by the Investigator based on response evaluation criteria in solid tumours (RECIST) v1.1 or by changes in tumour-derived blood biomarkers.
 
Haematologic malignancies cohort: To assess the efficacy of SUPLEXA in subjects with haematologic malignancies (multiple myeloma, lymphoma, and chronic lymphocytic leukemia).
 
	
 
Objective response rate (ORR) defined as the proportion of subjects with best overall response (BOCR) of either a complete response (CR) or partial response (PR).
 
Time to Progression (TTP).
 
Objective response rate as defined by standard of care.
 

Exploratory 
 
Exploratory efficacy outcomes
 
	
 
Duration of Response (DOR)
 
Time to Response (TTR)
 
Clinical Benefit Rate (CBR) defined as CR + PR + stable disease (SD).
 
Progression-free Survival (PFS).
 
Overall Survival (OS).
 
Solid tumours cohort: Change in plasma biomarkers.
 
Haematologic malignancies cohort: Response-relationship with correlative biomarkers in blood and bone marrow including immunophenotyping of circulating PBMC and/or bone marrow, gene expression, mutational analysis.
 

Objectives	Endpoints

 
• To evaluate anti-tumor activity of SUPLEXA by based on modified RECIST v1.1 for immune based therapeutics (iRECIST)
 
	
 
• iORR
 
• iPFS
 
• iDOR
 
• iDCR
 

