##### **4.1.2.1 First 3 SUPLEXA infusions (from batch 1)**

Initially, SUPLEXA will be administered at Day 1 (baseline), Week 1 and Week 2 (Section [1.2](#), [Figure 2](#)). The first 3 subjects in each cohort will be monitored closely at the clinic after each of these 3 weekly infusions with follow-up phone calls as described below.

The first 3 subjects in each cohort will be enroled and subsequently dosed in a staggered manner, at least 1 week apart to allow for evaluation of safety. These subjects will be monitored for safety in the clinic for 6 hours after each of the 3 weekly infusions and be contacted by phone on a daily basis (weekdays) between these weekly infusions and for up to 5 days post final treatment. While the Investigator will review safety data on a continual basis, the DSMB will have an opportunity to review the first 3 patients in each cohort who receive at least 3 doses of SUPLEXA to further evaluate safety and make a recommendation to the Sponsor concerning continuation or enrolment, pause in enrolment or study termination. While the DSMB reviews the data from the first 3 subjects in each cohort, additional subjects will be screened and enroled into each cohort. These additional subjects will not be dosed until the first 3 subjects in their cohort are cleared by the DSMB. These subjects will be monitored closely at the clinic for at least 3 hours after each of these 3 weekly infusions with follow-up phone calls every 2 business days between treatments and for up to 5 days post the 3rd infusion. If any of these subjects experience an adverse event of Grade 3 or greater, the longer in-clinic monitoring window of 6 hours post each of the first 3 weekly infusions and daily calls will be reimplemented as done for the first 3 subjects. During the observation period post SUPLEXA administration, subjects will be monitored for any AEs and immediate post infusion reaction(s) every 90 minutes.

The first 15 subjects in the trial will be evaluated for DLTs twice, 1 week after the 1st and 2nd dose (prior to administration of 2nd and 3rd dose, respectively). The DLT criteria and DLT assessment period(s) are defined in Section [6.5](#).

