#### 4.1.2.3 Disease Evaluation

For subjects in the solid tumours cohort, the on-treatment radiographic assessments of chest, abdomen, and pelvis will be performed per standard of care intervals throughout the course of the study.

The first radiographic scan after receiving SUPLEXA will be performed at Week 6-12 weeks after the 1st SUPLEXA infusion and thereafter every 6-12 weeks depending on tumour type and as clinically indicated per investigator's discretion.

These scans should be available for assessment by the Sponsor, if requested. The response evaluation will be assessed by the Investigator according to RECIST v1.1 and iRECIST until unequivocal radiographic disease progression, or until the subject starts a subsequent anticancer therapy (whichever comes first). The tumour assessment (imaging) for confirmation of response should be performed no less than 4 weeks after the criteria for response are first met. All radiographic scans will be collected and held for possible future retrospective evaluation by BICR.

For subjects in the haematological malignancies cohort, disease evaluation will be conducted every 4 weeks, as clinically indicated throughout the study.

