### 8.1 EFFICACY ASSESSMENTS

Planned time points for all efficacy assessments are provided in the SoA (Section 1.3).

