#### 8.1.2 Disease Response Assessments (Haematologic Malignancies Cohort only)

Haematologic malignancies (multiple myeloma, lymphoma, and chronic lymphocytic leukemia) disease response will be assessed by the Investigator every 4 weeks ( $\pm 3$  days) per standard of care.

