### **Haematologic malignancies Cohort**

Statistical analyses will be descriptive and graphical in nature. If sample size permits, complete remission will be summarized descriptively using Kaplan-Meier medians and quartiles.

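### Haematologic disease evaluation has three conflicting rules, and the schedule that sites are referred to fixes no evaluation by calendar between screening and EOS/ET

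*Combined protocol and SAP*

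**What the plan says.** Four places set the timing of one assessment, and they follow three different rules.

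- **Section 8.1.2** is mandatory: "disease response will be assessed by the Investigator every 4 weeks", with a window of ±3 days and reference to standard of care. It does not say when the count starts.
- **Section 4.1.2.3**, with the same sentence in the synopsis under Disease Evaluation, combines an obligation with a condition: "disease evaluation will be conducted every 4 weeks, as clinically indicated throughout the study".
- **Section 1.3 (SoA)**, in the row "Disease evaluation for haematologic malignancies only", has an unmarked X at screening and at EOS/ET. The cells between them carry an asterisk, explained as "As clinically indicated, may also be conducted every 4 weeks", with the start set at 4 weeks after the third dose.

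Section 8.1 adds: "Planned time points for all efficacy assessments are provided in the SoA".

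The endpoint worded for this cohort in Section 3 is "Objective response rate as defined by standard of care". Section 9.3.2 plans a descriptive analysis in which, if numbers allow, "complete remission will be summarized descriptively using Kaplan-Meier medians and quartiles". Section 3 also lists DOR, TTR, CBR, PFS and OS as exploratory endpoints without restricting them to solid tumours.

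**The concern.** A response can only be counted if someone looks for it, and it can only be dated to the day they looked. Under the SoA note, whether and when a haematologic subject is evaluated during treatment is left to the investigator. Under Section 8.1.2 it is fixed by the calendar. Two sites could each follow a rule in the protocol and evaluate similar subjects at very different frequencies.

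Objective response would then depend partly on how often each subject was assessed. A response that came and went between evaluations would not be recorded, and one that lasted would be dated late. The Kaplan-Meier quartiles for complete remission, and exploratory TTR, DOR and PFS, would carry the same uneven dating.

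The solid-tumour cohort does not have this gap. The same table bounds its scans: the first at 6 to 12 weeks after the first infusion, then every 6 to 12 weeks. Section 7.2 continues tumour assessment after discontinuation on the schedule that the protocol specifies, but for the haematologic cohort there is no single such schedule.

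**Working it through.** The plan gives no figure of its own to reproduce. The check compares the rules and then counts evaluations.

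**Inputs**

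- Doses 1 to 3: "SUPLEXA will be administered at Day 1 (baseline), Week 1 and Week 2" (Section 4.1.2.1). The SoA window is ±2 days, so dose 3 falls on Day 15 ± 2.
- Maximum treatment period: up to 24 weeks with two full batches (synopsis, Study Duration), taken as stated.
- Follow-up: every 8 weeks for 48 weeks after the last dose (synopsis and Section 4.1.3).
- Delay allowed for a DLT to resolve before the next dose: up to 3 weeks (Section 6.5.1).

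**Start point under the SoA note**

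- Day of dose 3 + 28: 13 + 28 = Day 41; 15 + 28 = Day 43; 17 + 28 = Day 45.
- In weeks from Day 1: (41 − 1)/7 = 5.7; (43 − 1)/7 = 6.0; (45 − 1)/7 = 6.3. The start is about Week 6 for an undelayed subject.
- With one full 3-week DLT delay: 2 + 3 + 4 = Week 9. The SoA start moves with dosing delays.

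**Evaluations in a 24-week treatment period**

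| Rule followed | Weeks of evaluation | Number |
|---|---|---|
| Section 8.1.2, counted from dose 1 (assumed) | 4, 8, 12, 16, 20, 24 | 24/4 = 6 |
| SoA, 4-weekly option used | 6, 10, 14, 18, 22 | 5 |
| SoA note, minimum required | none | 0 |

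The synopsis and Section 4.1.2.3 cannot be given a single count. It is 6 if the 4-weekly clause governs and as few as 0 if clinical indication governs.

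**Follow-up**

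- A 4-weekly interval needs 48/4 = 12 evaluations. The 8-weekly visits supply 48/8 = 6.
- A subject who receives only the first three doses has the last one at Week 2 and the first follow-up visit at 2 + 8 = Week 10. The SoA's optional Week 6 evaluation falls between visits. The follow-up rule therefore matters even for the shortest treatment course.

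**Which rule would a site follow?** Section 8.1 refers to the SoA for efficacy time points, and Section 8 calls adherence to SoA requirements essential. Section 8.1.2 sits directly under Section 8.1 and says something stricter. No order of precedence is stated.

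In the text available for this review the SoA columns are not aligned, so the exact visit under each asterisked cell is uncertain. The note itself and the unmarked first and last cells are legible.

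**The case against.** The strongest reply is that Section 8.1.2 is clear and mandatory, and that a site following the whole protocol must meet it whatever a footnote permits. Section 8 requires adherence to the study requirements, those in the SoA included, but does not rank the SoA above the text. The synopsis, Section 4.1.2.3 and Section 8.1.2 all state a 4-weekly interval, so the outlier is one table note. The cohort's analysis is only descriptive.

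Much of this stands: the problem is an inconsistency, not a decision to have no schedule. It does not remove the problem, because Section 8.1 sends the reader to the table with the weakest rule, and two of the other three places add the same condition. A descriptive response rate still depends on who was assessed and when.

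A reader might infer more than the documents support:

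- **That this is the cohort's only efficacy endpoint.** It is the secondary endpoint worded for this cohort. Exploratory endpoints also apply, and OS needs no disease evaluation.
- **That subjects are evaluated only when symptoms appear.** Screening and EOS/ET evaluations are unconditional, and clinical indication is wider than symptoms. Scheduled blood counts and chemistry could prompt an evaluation in a well subject.
- **That data from different sites cannot be pooled.** They can be, but with unequal ascertainment.
- **That treatment extension depends on these evaluations.** Sections 1.1 and 4.1.2.2 list safety status, clinical benefit and exploratory outcomes as alternatives.
- **That the response rate shifts by a known amount.** With about 8 subjects, one response is 1/8 = 12.5 percentage points. That becomes a bias only if a response is missed altogether, and one lasting to EOS/ET would be found there.

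**Conclusion.** The conflict is real and is in current text: one assessment is mandatory, conditional or optional depending on where one reads. The size of the gap is 6, 5 or 0 evaluations over a 24-week treatment period. The 6 rests on counting from dose 1, which Section 8.1.2 does not state. The 24 weeks is a best-yield maximum, and shorter courses reduce the first two counts. The 0 holds for any treatment length.

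The consequence is that objective response, the timing of complete remission and the exploratory response and progression endpoints have no fixed on-treatment schedule in this cohort and may be ascertained unequally across subjects and sites. The documents do not allow the effect on the response rate to be estimated. The point should be settled before further subjects are evaluated, because an assessment that was not made cannot be recovered at analysis.

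**What to change.** Reconcile the synopsis, Section 1.3, Section 4.1.2.3 and Section 8.1.2 to one rule:

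- a mandatory calendar schedule during treatment and during the gap between batch 1 and batch 2;
- one start point, one interval and one window, worded identically in all four places (Section 8.1.2 already states 4-weekly, ±3 days);
- clinical indication kept only for evaluations additional to that schedule;
- an explicit interval for follow-up, where visits are 8-weekly.

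On the start point, counting from dose 1 has a statistical advantage: it does not move when a dose is delayed, whereas counting from dose 3 does.

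During treatment the cost is mainly wording, since Section 8.1.2 already calls for the 4-weekly assessment. Sites that had relied on the optional note would do more routine evaluations. If the 4-weekly interval is carried into follow-up, about 12 evaluations are needed against 6 scheduled visits, so about 6 would fall between visits. The sponsor should either accept that burden or state a longer follow-up interval and take its coarser dating into account in the analysis.

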### **Screening Period – All Subjects**

Prior to enrolling in the study, and before performance of any procedures, potential subjects will attend a Screening session where they will be provided with full information concerning details of the study assessments and procedures. They will also be provided with a Participant Information Sheet and Informed Consent Form (PICF). Prior to being required to sign the consent form, subjects will be given time to review study information and ask questions.

After signing the PICF, potential candidates will undergo screening procedures over 2 visits during a Screening period lasting up to 5 weeks (Section [1.2](#), [Figure 1](#)). During Screening Visit 1, blood will be drawn for safety laboratory assessment (~5 mL), for processing and manufacturing of SUPLEXA batch 1 (~50 mL of whole blood) and for exploratory studies (~20 mL of whole blood). Subjects who meet the safety laboratory inclusion criteria and have adequate evidence of blast formation at the manufacturing facility (notification of status will require 5 days from the initiation of culture), will proceed to Screening Visit 2. Subjects in whom the SUPLEXA blast formation does not occur will be considered screen failures and be replaced. This is expected to be < 10 % of subjects.

Standard of care tests/procedures that were performed prior to signing the consent can be used as part of the screening assessments if the procedures meet the protocol-required timelines (i.e., within 5 weeks of consent) and it is documented in the source documents that these procedures performed prior to signing the consent were standard of care procedures.

Eligibility criteria for study entry will be assessed locally by the Investigator; for the solid tumour cohort, screening radiographic scans (within 5 weeks of consent) will be collected and held for possible future retrospective evaluation by Sponsor or blinded independent central review (BICR). Safety laboratory assessments of all subjects will be rechecked for eligibility on the day of the first treatment with the local hospital laboratory (and the central laboratory for documentation), prior to first dose with study intervention.

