## 1.3 SCHEDULE OF ACTIVITIES

Study period	Screening		Treatment Period (Weekly dosing)		TREATMENT GAP	Treatment Extension Period	Follow Up after last dose		Notes	
			SUPLEXA Batch 1							
Study Treatment Week	-5	-5 to -1	First 3 infusions	Additional doses 		Batch 2				
Visit Window (days)		±2		±2		Doses 	Every 8 weeks up to 48 weeks from last dose	EOS/ET		
Informed consent	X									
Demographic and medical history	X a								a. Medical history of the prior 3 years including any co-morbid conditions requiring active treatment and significant surgeries.	
Inclusion/Exclusion	X	X								
Solid tumour/haematologic malignancy diagnosis confirmation and disease staging	X b								b. Radiology reports and photography images from imaging that occurred within 4 weeks of signing informed consent and throughout the study should also be noted as available for later access by Sponsor (if required).	
History of prior anti-cancer therapy		X c							c. Information on all interventions (systemic therapy, surgery, radiation treatment) related to the subject's cancer will also be collected. Prior immunotherapy dosing concentration and cycle numbers should be captured.	
Prior & concomitant medications		X	X	X	X	X	X	X		

Study period	Screening		Treatment Period (Weekly dosing)		TREATMENT GAP	Treatment Extension Period	Follow Up after last dose		Notes	
			SUPLEXA Batch 1							
Study Treatment Week	-5	-5 to -1	First 3 infusions	Additional doses 		Doses 				
Visit Window (days)		±2		±2		60	-1 to +7	±5	±28	
Survival status and subsequent anticancer therapy								X d	X d	d. Beyond Week 48, subjects enrolled in the trial may be contacted every 12 weeks up to a maximum of 24 months after the last dose of SUPLEXA or earlier if the study is terminated by the Sponsor.
Physical exam and height e	X		X	X f	X f		X f	X	X	e. Height at screening only f. Symptom-directed physical exam
Vital signs and weight	X		X	X	X		X	X	X	
Performance status	X		X	X	X		X	X	X	Eastern Cooperative Oncology Group (ECOG) for solid tumours; Karnofsky for haematologic malignancies.
Electrocardiogram (ECG)		X	X	X g	X g		X g		X	g. As clinically indicated

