Syphilis screening test		X							m. HIV positivity is disqualifying as this might be amplified in ex vivo stimulation	
Pregnancy test (WOCBP only)		X							Women of childbearing potential (WOCBP) Negative test must be performed within 72 hours prior to first study intervention	
Urinalysis		X	X n			X n			Refer to Table 5 for list of parameters to be evaluated	
Blood sample for SUPLEXA manufacturing	X o				X p				o. Batch 1: Subjects who will have adequate evidence of blast formation at the manufacturing facility (notification of yield will be 5 days after the blood collection), will proceed to next Screening	

Study period	Screening		Treatment Period (Weekly dosing)		TREATMENT GAP	Treatment Extension Period	Follow Up after last dose		Notes	
			SUPLEXA Batch 1							
Study Treatment Week	-5	-5 to -1	First 3 infusions	Additional doses 		Batch 2				
Visit Window (days)		±2		±2		Doses 	Every 8 weeks up to 48 weeks from last dose	EOS/ET		
Pre-treatment prophylaxis			X	X	X				visit. Subjects with insufficient yields will be considered screen failures and will be replaced.	
SUPLEXA administration IV			X q	X q	X r		X r		
p. Batch 2: After completion of Batch 1 and if subjects are eligible to continue to receive SUPLEXA, batch number 2 manufacturing and processing will take place.
 
The following pretreatment regimen is suggested, although a different regimen based on local standard of care/institutional practices is permitted: Administer acetaminophen 1000 mg (PO) for potential fever, diphenhydramine 12.5 mg PO (for potential rash) and allopurinol (100 mg) IV or PO for potential TLS in subjects who are at intermediate risk for TLS approximately 1 hour (60 min ± 20 min) before SUPLEXA infusion. Refer to Section 6.8.1 and 10.8Section 10.8 for further details.
 
q. Weekly 2.5 billion cells r. Additional treatment every 2 weeks at 5.0 B cells will be the investigator's assessment and in
	

Study period	Screening		Treatment Period (Weekly dosing)		TREATMENT GAP	Treatment Extension Period	Follow Up after last dose		Notes	
			SUPLEXA Batch 1							
Study Treatment Week	-5	-5 to -1	First 3 infusions	Additional doses 		Batch 2				
Visit Window (days)		±2		±2		Doses 				
			Week 0 Day 1/ Baseline	1, 2			Every 8 weeks up to 48 weeks from last dose	EOS/ET		

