#### Type of Subject and Disease Characteristics

##### Solid Tumours

2. Histologically or cytologically confirmed diagnosis of locally advanced or metastatic solid tumour.
3. Have 1 or more tumours measurable based on RECIST v1.1 as assessed by the local site Investigator. Radiographic scans should be obtained within 5 weeks of Screening. Lesions situated in a previously irradiated area are considered measurable if objective progression has been demonstrated following radiation to such lesions.
4. Subjects who did not attain a durable response after receiving at least one standard/approved therapies which may include chemotherapy, targeted agents, radio-, immuno- conjugates, check point inhibitors or where there is no approved therapy. This includes subjects who attained a long-term stable disease (SD), or partial response (PR) are eligible. Long term SD subjects on a checkpoint inhibitor may continue checkpoint inhibitor (CPI) therapy.  
\* Any therapies defined as immunosuppressive require a washout period of at least 4 weeks, defined as 4 weeks (28 days) prior to blood collection for SUPLEXA manufacturing and any SUPLEXA dose administration.

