#### **Medical Conditions**

1. Known central nervous system (CNS) metastases and/or carcinomatous meningitis.
2. Prior allogeneic transplant.
3. Diagnosis of immunodeficiency or is receiving chronic and non-physiological, systemic steroid therapy or any other form of immunosuppressive therapy.
4. Active uncontrolled bacterial, viral, or fungal infection requiring systemic therapy at screening or Day 1.
5. History or current evidence of any condition, therapy, or laboratory abnormality that might confound the results of the study, interfere with the subject's participation for the full duration of the study, or is not in the best interest of the subject to participate, in the opinion of the treating Investigator.
6. Any unresolved Grade 2 or greater reversible toxicity from a previous anticancer therapy except for alopecia or Grade 2 neuropathy.
7. Clinically significant cardiovascular disease, including any of the following:

- a. Stroke or myocardial infarction within 6 months prior to first dose in the study.
- b. Presence of unstable angina within 6 months prior to first dose in the study.
- c. Congestive heart failure of New York Heart Association Grade 2 or higher.
- d. History or presence of clinically significant ventricular arrhythmias, or conduction abnormality; presence of clinically significant atrial fibrillation and resting bradycardia.
- e. Corrected QT interval (QTcF) of  $>450$  msec (males) or  $>470$  msec (females) using Fridericia's correction formula.
- f. History of congenital long QT syndrome.

8. Known history of testing positive for human immunodeficiency virus (HIV), and/or positive test for Hepatitis B virus surface antigen (HBsAg) and/or positive Hep C antibody result with detectable hepatitis C virus (HCV) ribonucleic acid (RNA) indicating acute or chronic infection.

*Note: Subjects who have been vaccinated against Hepatitis B and hence are positive only for the Hepatitis B surface antibody are permitted to participate in the study.*

9. A serious non-malignant disease (e.g., psychiatric, substance abuse, uncontrolled intercurrent illness, etc.) that could compromise protocol objectives in the opinion of the Investigator and/or the Sponsor.

10. At high risk of developing TLS per ([Cairo, 2010](#)). Specifically:

- a) Burkitt's lymphoma
- b) ALL with LDH  $\geq 2 \times \text{ULN}$  or WBC  $\geq 100 \times 10^9$  per  $\mu\text{L}$ .
- c) AML with WBC  $\geq 100 \times 10^9$  per  $\mu\text{L}$ .

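### HIV serology is scheduled only after culture of the manufacturing blood has begun, too late for an undiagnosed subject to prevent the amplification that the protocol gives as its reason

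*Combined protocol and SAP*

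**What the plan says.** The screening text (Section 1.1, Screening Period, repeated almost unchanged in Section 4.1.1) describes two visits. For the first: "During Screening Visit 1, blood will be drawn for safety laboratory assessment (~5 mL), for processing and manufacturing of SUPLEXA batch 1", the manufacturing draw being about 50 mL, with a further sample for exploratory work. Those who go on to the second visit are "Subjects who meet the safety laboratory inclusion criteria and have adequate evidence of blast formation at the manufacturing facility", and that status is known 5 days after culture is started. Subjects without blast formation are screen failures and are replaced; fewer than 10% are expected.

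The Schedule of Activities (Section 1.3) has two screening columns, week -5 and weeks -5 to -1.

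- The row "Blood sample for SUPLEXA manufacturing" is marked for batch 1 in the first column. Its note o begins "Subjects who will have adequate evidence of blast formation at the manufacturing facility" and sends these subjects on to the next screening visit.
- Serology is marked once, in the second column, with note m: "HIV positivity is disqualifying as this might be amplified in ex vivo stimulation". Table 5 (Section 10.2) lists its contents as HIV antibody, HBsAg, and HCV antibody or RNA.
- The row "History of prior anti-cancer therapy" and the row for prior and concomitant medications are first marked in the second column.
- Inclusion/Exclusion is marked in both columns, and medical history in the first.

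Among the eligibility criteria, exclusion 8 (Section 5.2) opens with "Known history of testing positive for human immunodeficiency virus (HIV" and then covers hepatitis B and C by test result. Under inclusion 4 (Section 5.1), immunosuppressive therapies "require a washout period of at least 4 weeks, defined as 4 weeks (28 days) prior to blood collection for SUPLEXA manufacturing", and also before any dose. A note to exclusion 17 asks for 14 days since the last investigational agent before the study blood is drawn.

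**The concern.** Note m ties the HIV exclusion to something that happens during manufacture. A control on that hazard should act before manufacture starts. As scheduled, a subject who does not know that they are infected gives blood at Visit 1, the cells are stimulated and expanded, and the first planned HIV test follows.

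Three things are at stake: amplification of virus in culture, a draw of about 50 mL that served no purpose, and a batch that cannot be given. A smaller issue sits beside this. Two eligibility criteria count back from the blood draw, but the rows that record the supporting therapy data are scheduled one visit after it.

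**Working it through.** No sample-size or error-rate figure is involved. The check sets the screening text, the Schedule of Activities and the eligibility criteria side by side.

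1. **Order of visits.** The week labels of the two screening columns overlap, so they do not settle the order by themselves. The text does: Visit 2 follows the blast result. Note o says the same, and consent, blood count and manufacturing blood all sit together in the first column.

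2. **Start of culture.** The screening text counts the 5 days from the start of culture; note o counts 5 days from blood collection. Taken together, culture starts at about the time of collection. The protocol text contains no step that holds a sample until serology is back.

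3. **Timeline.** Day 0: Visit 1 draw and start of culture. About day 5: blast status reported. Day 5 or later: Visit 2, with HIV serology. After that: Day 1 dosing. The scheduled HIV result therefore comes at least about 5 days after ex vivo stimulation began, and before any infusion.

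4. **What Visit 1 can catch.** The Inclusion/Exclusion review and medical history at Visit 1 can identify a known HIV infection through exclusion 8. They cannot identify an unknown one. The conditions for reaching Visit 2 are the safety laboratory criteria and blast formation; serology is not among them.

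5. **Note m against exclusion 8.** Note m disqualifies on positivity. The HIV limb of exclusion 8 refers to a known history. A first positive result at Visit 2 is disqualifying under note m but not clearly under exclusion 8.

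6. **Draw-anchored criteria.** Inclusion 4 looks back 28 days from day 0, and the note to exclusion 17 looks back 14 days from the draw. The therapy-history and medication rows that document both fall at about day 5 or later, while the eligibility review that applies them is already marked at day 0.

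**The case against.** The strongest reply is that note m can be read as protecting the recipient: HIV disqualifies because amplified virus must not be infused. On that reading, serology at any time before Day 1 is enough. This stands as far as dosing goes. It does not make the Visit 2 timing sensible, because the stated hazard arises in culture and the draw and batch are spent by then.

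Other safeguards can be cited:

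- Standard-of-care results obtained before consent may be used for screening. That is permitted, not required.
- Exclusions 3 and 5 (immunodeficiency, and laboratory abnormalities judged to confound) could remove a subject newly found positive. They too act only once the result exists.
- Table 5 lists serology under safety laboratory tests, so it might be thought part of the Visit 1 safety bloods. The Schedule of Activities puts the two in separate rows at separate visits, and even on this reading nothing delays culture until the result arrives.
- Section 2.2.1 refers manufacturing and release criteria to the Investigator's Brochure, and the Figure 1 schema is not reproduced. Incoming testing or quarantine at the facility may therefore exist. This stands as a limit: the point concerns what the protocol schedules, not what the facility does.

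On prior therapy, the reply is largely right. The eligibility review and medical history at Visit 1 let a site check the washout before drawing blood.

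**Conclusion.** The point holds for HIV. For a subject with undiagnosed infection, the only scheduled HIV test follows the step whose hazard is given as its reason, by at least about 5 days. Exclusion 8 and note m also disagree on what disqualifies. The conclusion rests on the column positions in the Schedule of Activities, which agree with the screening text, and on culture starting at about the time of collection.

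A reader might infer more than the documents support:

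- **That infected subjects could be dosed through this gap.** Visit 2 serology still precedes Day 1 and can bar dosing.
- **That hepatitis timing has the same fault.** Note m gives the amplification reason for HIV only, so Visit 2 hepatitis testing contradicts nothing.
- **That the pre-draw washout cannot work.** It can be checked at the Visit 1 review. What is missing at that point is the scheduled record behind it.
- **That a number of infected cultures can be given.** No prevalence is stated, and any figure would rest wholly on an assumed one.

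This should be fixed. It does not rank higher, because no endpoint, analysis set or pre-infusion check is affected.

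**What to change.** 1. In the Schedule of Activities, move the serology row to Screening Visit 1; hepatitis moves with the panel. Amend Sections 1.1 and 4.1.1 to match.
2. State that culture does not start, or that the sample is held in quarantine, until the HIV result is available. If the facility already does this, say so.
3. Reconcile exclusion 8 with note m so that a positive screening test is covered.
4. As a secondary alignment, move prior anti-cancer therapy history and prior medications to Visit 1, so that the record for inclusion 4 and the exclusion 17 note exists when the Visit 1 eligibility review is done.

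The tests and forms are already planned and move one visit earlier, to a visit at which blood is drawn anyway. The added cost is serology on subjects who then fail blast formation. At the protocol's ceiling of 10%, and taking the planned 60 as subjects who pass, 60 / 0.9 = 66.7 cultures, so fewer than 66.7 - 60 = 6.7, or about 7, extra panels over the whole study. Subjects who fail the Visit 1 safety laboratory criteria would add to this; the documents give no figure for them. There may also be a short wait for the HIV result before culture proceeds.
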